Appendix A

Screening, Recruitment, and Enrollment

A1: Eligibility Screening for Hopelessness

Indicate yes or no whether the following inclusion criteria are met for the study:

Inclusion Criteria	Yes	No
≥18 years old		
Diagnosed with MI, unstable angina, who underwent percutaneous coronary intervention (PCI) or coronary artery bypass graft (CABG) surgery		
Speaks and reads English		
Can complete the screening instrument		

If “yes” to all the above criteria, patient is eligible to be screened for hopelessness (see state scale of State-Trait Hopelessness Scale on next page)

State Hopelessness: Screening and Scoring

Today (Right now)...

1. Today, it is difficult for me to imagine my future.	Strongly disagree 1	Disagree 2	Agree 3	Strongly agree 4
2. Today, I believe I cannot make a difference.	Strongly disagree 1	Disagree 2	Agree 3	Strongly agree 4
3. Today, I believe that things will improve.	Strongly disagree 4	Disagree 3	Agree 2	Strongly agree 1
4. Today, I believe I am powerless to change my future.	Strongly disagree 1	Disagree 2	Agree 3	Strongly agree 4
5. Today, I see my future as gloomy.	Strongly disagree 1	Disagree 2	Agree 3	Strongly agree 4
6. Today, I believe I will accomplish what I set out to do.	Strongly disagree 4	Disagree 3	Agree 2	Strongly agree 1
7. Today, I believe I can help improve things.	Strongly disagree 4	Disagree 3	Agree 2	Strongly agree 1
8. Today, I feel giving up would be easier.	Strongly disagree 1	Disagree 2	Agree 3	Strongly agree 4
9. Today, I believe I can overcome obstacles.	Strongly disagree 4	Disagree 3	Agree 2	Strongly agree 1
10. Today, things will not work out as I would like.	Strongly disagree 1	Disagree 2	Agree 3	Strongly agree 4

Steps to score:

- 1) Add 10 item scores, to get a total (NOTE that reverse-scored items have different values in bold above). TOTAL SCORE = _____ Divide total by 10 to get a final score. FINAL SCORE = _____
- 3) Repeat steps 1 and 2 to confirm final score
- 4) If FINAL SCORE is 1.8 or greater, patient is eligible for the [name] study. If FINAL SCORE is less than 1.8, patient is eligible for the student's study

A2: Exclusion Criteria for Enrollment in PI's Study

Indicate yes or no whether the following exclusion criteria are met for the study:

Exclusion Criteria	Yes	No
Younger than 40 or older than 80 years of age		
Has a pacemaker or implanted cardioverter-defibrillator		
Has a chronic arrhythmia		
History of or current valvular disease		
History of organ transplant		
Current use of immunosuppressive medications		
Diagnosed with diabetic autonomic insufficiency		

If "no" to all the above criteria, patient is eligible to enroll in the PI's study

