3.0 Eligibility

3.1 Inclusion Criteria

- Eligibility criteria for hopelessness screening include: Adults \geq 18 years old; diagnosed with myocardial infarction, unstable angina, or who undergoing percutaneous coronary intervention or coronary artery bypass graft surgery; speak and read English; and can complete the screening instrument.

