3.2 Exclusion Criteria

- The following exclusion criteria are in place because they alter heart rate variability: having a pacemaker or implanted cardioverter-defibrillator, chronic arrhythmia, history or current valvular disease, history of organ transplant, current use of immunosuppressive medications, or diabetic autonomic insufficiency. Although research conducted in 2016 identified HRV diminishing with age when controlling for disease and medication use, more recent research has identified no relationship between HRV and age. A study of healthy individuals, controlling for other health conditions, did not find any relationship between resting HRV and age in adults older than 40. Another study of healthy participants identified no significant difference in resting HRV between persons in the age group 40-49 compared to 50-59. Because the median age for a male with IHD is 65 years and for females is 70 years, the age range of 40-80 years was chosen to be representative of the IHD population and to mitigate the confounding effect of age on HRV.

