4.0 Subject Enrollment

The PI will screen potentially eligible patients over the phone or in person. Screening will include asking patients if they meet any of the exclusion criteria described above. Patients who are eligible for enrollment after screening will be asked by the PI to participate in the proposed research. The PI will read through a script to describe the study. If a patient agrees to enrollment in the study, written consent will be obtained. If the participant is enrolled after hospital discharge, they will be sent a link via email or text message, which will take them to the REDCap e-consent page, where they will provide an electronic signature. After the electronic signature is accepted and confirmed, a copy of the signed e-consent will be sent to the patient by email and/or postal mail and a copy will be saved in the REDCap database.

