Heart Rate Variability Procedures. At Week 2, participants will be instructed to place the Polar H7 heart rate monitor around the center of their chest, in contact with the skin, and the ActiGraph wGT3X-BT around their waist, according to directions outlined in the written instructions provided and as demonstrated in the instructional video and practiced with the applicant over the phone. Participants will be informed that the monitors are used to gather data about their body at rest. The Polar H7 heart rate monitor connects to the ActiGraph with Bluetooth® wireless technology so that the interval between normal heart beats (RR data) can be transferred to csv files for analysis. The HRV protocol will take place during a 10-minute time period on two consecutive days, to ensure at least one 10-minute time frame of usable data. Participants will be instructed to place the monitors first thing in the morning after they wake up and empty their bladder. Once the monitors are placed, participants will be instructed to lay supine quietly for 10 minutes and avoid moving or using any devices or watching tv. The standardized HRV protocol improves reliability of the HRV measurement because control of extraneous variables is maintained. Respirations will not be controlled because this can artificially increase HF HRV. The gold standard amount of time for a short-term HRV recording is 5 minutes. The 5 minutes of the recording with the least amount of artifact will be used for analysis. After 10 minutes of recording are completed, the heart rate monitor and ActiGraph will be removed. After the participant completes the 10-minute HRV measurements on two consecutive days, they will be asked to return the monitors in a prepaid envelope that will be

picked up from their mailbox by USPS and returned to the PI, mitigating any exposure to COVID-19.

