State-Trait Hopelessness Scale (STHS)	State and trait hopelessness	Week 2	23	1-4	
 4-point Likert-type scale: 1 = strongly disagree, 4 = strongly agree Differentiates state and trait hopelessness Adding the item scores and dividing by the number of items provides a total score for each subscale 	
 Reliability: state $\alpha = 0.87$, trait $\alpha = 0.87$ Concurrent and predictive validity with IHD patients
ENRICH Social Support Inventory (ESSI)	Perceived social support	Week 2	5	5-25	
 5-point Likert-type scale: 1 = none of the time, 5 = all of the time Items summed for score: higher scores indicate greater perceived social support 	Found valid and reliable in patients with IHD
Patient Health Questionnaire -9 (PHQ-9)	Depressive symptoms	Week 2	9	0-27	
 Measures depressive symptom severity Items scored on a Likert-type scale from 0 = not at all to 3 = nearly every day and summed for a total score Separate cognitive and somatic depressive symptoms dimensions have been validated in patients with IHD 	Internal reliability and criterion and construct validity previously established
Medical Records Abstraction Form	Clinical characteristics	Hospital	5	NA	
 Two purposes: 1) To confirm eligibility and 2) To collect diagnoses, cardiovascular procedures, and admission height and weight 	NA

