8.0 Data Analysis

Data Analysis for Each Aim. Confirmation of the internal reliability of scales will be assessed using Cronbach's alpha. The following analyses will be used for each aim.

Aim 1: Kubios HRV software will be used to generate the HRV data for time, frequency, and nonlinear domain analyses. Kubios uses a threshold-based artifact correction algorithm that compares RR beats against a local average interval. The lowest level threshold that accurately detects artifact without overcorrecting normal beats will be used for each recording. Recordings with >5% artifact will not be used in analysis because even a small number of corrected ectopic or missing beats can have a great influence on short-term HRV results. To prevent the issue of not having useable data for a participant, participants are instructed to obtain the measurement at two separate timepoints. The recording with the least artifact will be used. The primary analysis for Aim 1 involves regressing hopelessness levels on HRV, after controlling for relevant demographic (e.g., age, sex) and other covariates (e.g., time of day, deviation from protocol,

etc.), using a multiple regression framework. All covariates as well as hopelessness and HRV levels will be normalized using transformations as needed; to ensure model robustness to variable distributions we will also apply rank-based approaches and bootstrapping of standard errors. As part of a sensitivity analysis, we will fit these same models within the two subgroups: those with moderate to severe hopelessness versus minimal to no hopelessness. Additional subgroup analyses will be completed to evaluate potential differences between sexes and type of IHD event and will include adding interaction terms to the models between sex or type of IHD event and HRV.

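### Only arrhythmia that is chronic at screening is excluded and the HRV exclusions are not reapplied at Week 2, so a later persistent irregular rhythm can, at a wide artifact threshold, be analysed as high HRV

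*Combined protocol and SAP*

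**What the plan says.** Section 3.2 lists conditions that are excluded because they alter HRV, among them "having a pacemaker or implanted cardioverter-defibrillator, chronic arrhythmia, history or current valvular disease". Appendix A2 repeats the arrhythmia item as "Has a chronic arrhythmia". Neither names a new, transient or paroxysmal rhythm.

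The exclusions are established in two ways. Section 4.0 states: "Screening will include asking patients if they meet any of the exclusion criteria described above". Table 1 in section 5.0 adds a hospital record form with two purposes: "1) To confirm eligibility and 2) To collect diagnoses, cardiovascular procedures, and admission height and weight". Section 5.0 has record data collected within two weeks of discharge.

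The population is patients "diagnosed with myocardial infarction, unstable angina, or who undergoing percutaneous coronary intervention or coronary artery bypass graft surgery" (section 3.1).

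At Week 2 the chest strap links to the activity monitor "so that the interval between normal heart beats (RR data) can be transferred to csv files for analysis". No ECG trace is planned. Section 8.0 describes the filter: "Kubios uses a threshold-based artifact correction algorithm that compares RR beats against a local average interval". On the setting it says: "The lowest level threshold that accurately detects artifact without overcorrecting normal beats will be used for each recording". Recordings with more than 5% artifact are dropped, and the cleaner of the two days is used; section 5.0 adds that the cleanest five minutes are analysed. Section 9.0 asks for a repeat when a recording is not appropriate, but does not define that word in terms of rhythm.

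**The concern.** By listing rhythm among its HRV exclusions, the plan accepts that an abnormal rhythm spoils the measure. It also describes the RR data as intervals between normal beats, but no planned step confirms this on the day of recording. A rhythm disturbance that begins after the infarction or operation is not chronic at screening, so the A2 item does not clearly catch it.

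The artifact rule was built for another task. It looks for beats that stand out from their neighbours. In a rhythm that is irregular throughout, few beats may stand out, and the variation left in the series is counted as HRV.

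HF HRV is the predictor in Aim 1 and the mediator in Aim 3. A few very large values have high leverage. If they are unrelated to hopelessness, they pull the slope toward zero. If they cluster in one hopelessness group, the bias can go either way. Aim 2 does not use HRV and is not affected.

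**Working it through.** The plan gives no power, effect size, numeric threshold or arrhythmia rate, so there is no stated figure to reproduce. The inputs from the documents are the 5% limit, the local-average rule and the planned 225 + 45 = 270 patients (section 1.0). Everything else below is an assumption.

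**Step 1: can an irregular rhythm pass the 5% limit?** Treat RR intervals as normally scattered about the local average with standard deviation s, and flag a beat when it deviates by more than c. Flagged share = 2 × (1 − Φ(c/s)).

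| s (s) | c (s) | c/s | flagged | 5% limit |
|---|---|---|---|---|
| 0.15 | 0.45 | 3.00 | 0.27% | passes |
| 0.15 | 0.35 | 2.33 | 1.96% | passes |
| 0.15 | 0.25 | 1.67 | 9.56% | fails |
| 0.18 | 0.35 | 1.94 | 5.2% | fails |
| 0.20 | 0.35 | 1.75 | 8.0% | fails |
| 0.25 | 0.45 | 1.80 | 7.2% | fails |

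Passing therefore needs a wide threshold and moderate irregularity. A simulation of 320-second RR series agrees (independent gamma intervals, mean 0.60 to 0.90 s, coefficient of variation 0.15 to 0.25, 11-beat local median). At a fixed 0.45 s, 61% to 100% of irregular recordings passed; at 0.15 s or tighter none did. Those that passed had HF power roughly 9 to 73 times the simulated sinus value.

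**Step 2: what would passing recordings do to Aim 1?** Let a share e of patients have transformed HRV shifted up by d SD, unrelated to hopelessness. Then observed r = r(1 − e) / √(1 + e(1 − e)d²). Power, two-sided 5%, is about Φ(|atanh r|·√(n − 3) − 1.96). Take true r = -0.20 and n = 270, so √267 = 16.34.

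- Clean: 0.2027 × 16.34 − 1.96 = 1.35, power 0.91.
- e = 1%, d = 3: r = -0.198/√1.0891 = -0.190, power 0.88.
- e = 6%, d = 4: r = -0.188/√1.9024 = -0.136, power about 0.61 (0.62 by simulation).

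The planned rank-based check must be compared with its own clean value. Simulated Spearman power is about 0.87 to 0.89 clean, about 0.86 to 0.87 in the 1% case and about 0.78 to 0.80 in the 6% case.

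**Step 3: sample size and direction.** The figure of 270 is an upper bound, because section 5.0 limits Aims 1 and 3 to parent-study patients who meet this study's criteria, plus the 45. In the planned within-group model for those 45, with an assumed true r of -0.30, two patients at +3 SD cut simulated power from 53% to 37%.

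If irregular recordings cluster, the error need not be conservative. Suppose the true r is 0 and four recordings at +3.5 SD all fall in the least hopeless sixth of 270, where mean hopelessness is about -1.5 SD. The covariance is (4/270) × 3.5 × (-1.5) = -0.078 and the HRV SD is about 1.09, so r is about -0.07. Simulation gave a 20% false-positive rate, in the hypothesised direction.

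**The case against.** The plan has more protection than the A2 checklist alone. Records are abstracted to confirm eligibility, so an arrhythmia diagnosed in hospital could be seen. Enrolment may follow discharge, so screening need not come before an early post-procedure arrhythmia. Recordings are reviewed on return and can be repeated. The threshold is judged for each recording, so somebody already looks at each series. The cleanest five minutes of the cleaner day are used, and rank-based methods are planned.

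Much of this stands. These steps lower the chance that an intermittent or already diagnosed arrhythmia gets through. They do not settle a persistent one: no rule says what to do about a non-chronic arrhythmia found in the records, the repeat rule does not mention rhythm, and choosing the cleanest segment does not help when every segment is irregular. Ranks soften the loss without removing it.

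Three stronger readings are tempting, and the documents do not support them.

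- **That nobody asks about rhythm at Week 2.** The script in Appendix B1 shows no rhythm question, but it contains an adverse-event block whose items are not shown, and section 11.3 defines adverse events broadly. Absence cannot be proved. What can be said is that nothing shown links such an answer to dropping the recording.
- **That an irregular rhythm will generally pass the filter.** Four of the six cases in the table fail, and section 8.0 gives no numeric threshold.
- **That Aim 1 loses a known amount of power.** No rate is given, and n = 270 is only a ceiling.

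It is also fair to say that classing rhythm from RR data alone is imperfect and can remove a genuine high-HRV recording.

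**Conclusion.** The gap is real but conditional. The arrhythmia exclusion is fixed at or near enrolment, the measurement comes later, and the single numeric filter is not a rhythm check. Whether a persistent irregular rhythm enters Aims 1 and 3 depends on a threshold set by judgement for each recording. The wording about not overcorrecting normal beats leaves room for a wide one.

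The size is unknown. Under the assumptions above, the effect runs from trivial (r from -0.20 to about -0.19, power 0.91 to 0.88) to material (r about -0.14, power about 0.62). The heavy end needs 6% of analysed recordings to be non-sinus, to escape the other checks and to pass the limit, and nothing in the documents supports that rate. This is a cheap improvement, not a flaw that invalidates the design.

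**What to change.** 1. In sections 8.0 and 9.0, before HRV is computed, have each RR tachogram and Poincaré plot inspected without sight of the hopelessness score, against a written criterion for a sustained irregular, non-sinus pattern.
2. Treat a recording that meets the criterion as not appropriate, whatever its artifact percentage: use the other day or ask for a repeat. If the pattern persists, leave the participant out of the primary Aim 1 and Aim 3 analyses.
3. Report the number so classed by hopelessness group, with a sensitivity analysis that keeps them.
4. In the Week 2 script, ask about any new irregular rhythm or new pacemaker or defibrillator since screening, and apply the HRV exclusions as of the recording date for Aims 1 and 3.

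The cost is one script question and a look at plots of data already loaded in the HRV software. A few recordings will be lost, and some may be genuine high values; the sensitivity analysis shows whether that matters. If data collection has finished, the blinded inspection and the sensitivity analysis can still be done from stored RR files.

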We will now complete the questionnaires together. Please find the hard copy of the questionnaires that were shipped to you so that you can read along. To complete the questionnaires, I will read each question to you and have you state your answer. I will chart your answers in our computer system. Do you have any questions before we begin?

Demographics and Characteristics

The first questionnaire will have you answer questions about yourself. (Ask patient the questions in questionnaire and chart answers in REDCap)

Self-Assessment Questionnaire (Hopelessness)

For the next questionnaire, please note that the first set of questions asks how you feel “today (right now)”, and the second set of questions asks how you feel “typically (over time). Also note that some of the questions are worded in a positive manner, and others are worded in a negative manner”. (Ask patient the questions in questionnaire and chart answers in REDCap)

Suicidal Ideation Screening

To be completed only if participant scores 1.8 or higher on the self-assessment questionnaire

The next few questions I ask will be used to assess your safety. (Complete suicide ideation questions with patient and following instructions in the virtual suicide protocol based on patient risk level).

Patient Health Questionnaire (PHQ-9)

We will move on to the next questionnaire. Over the last 2 weeks, how often have you been bothered by any of the following problems? (Ask patient the questions in questionnaire and chart answers in REDCap)

Enriched Social Support Instrument

The next set of questions assesses how you view your social support. The scale ranges from none of the time to all of the time. (Ask patient the questions in questionnaire and chart answers in REDCap)

Serious Adverse Events and Adverse Events

At the end of every visit, I like to check in and make sure you have not experienced any of the following since the research staff talked with you in the hospital or after your discharge home. (Complete questions).

Return Monitors and Compensation

Thank you so much for your time today! Please remember to place the two monitors in the prepaid return envelope. You can place the envelope in your mailbox and the postal service will pick it up. Once I receive the returned monitors, I will send you \$20 to thank you for participating in the study.

Do you have any questions about how to return the monitors or any other questions about the study?

Thank you for participation in the study!

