6.0 Expected Risks/Benefits

Potential Risks. There is minimal likelihood or seriousness of potential risks to participants. There are no identified physical, legal, or financial risks. Participants may become fatigued during completion of the study questionnaires and HRV monitoring and may feel apprehensive or distressed sharing information, but there is low probability of this and a low level of seriousness. There is potential for loss of confidentiality; however, procedures to protect against this risk will be put in place, as described below. Patients will continue to seek and receive standard medical care for their IHD diagnosis; therefore, any health care problems that may arise will be referred to their health care provider.

Protections Against Risk: The PI who will conduct remote data collection (by phone) 2 weeks after patients' hospital discharge, has been trained to assess for potential fatigue or apprehension of participants. If participants exhibit apprehension, they will be given the option to discuss this, to complete the questionnaires at another time, to be referred to their physician for further counseling follow-up, or to discontinue the study. These are all expected to be effective approaches. Patients will additionally be informed that they can withdraw from the study at any time, without loss of benefits they would otherwise be entitled to and without penalty to their health care. There is no risk for incidental findings.

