Appendix D

Data Collection Instruments

D1: State-Trait Hopelessness Scale

Self-assessment (State-Trait Hopelessness) Scale Part 1 of 2

DIRECTIONS: A number of statements, which people may use to describe their thoughts, are given below. Read each statement and then circle the response to the right of the statement that best describes how you are thinking today (right now). There are no right or wrong answers. All of your information will be kept confidential.

Today (Right now)...

1. Today, it is difficult for me to imagine my future.	Strongly disagree	Disagree	Agree	Strongly agree
2. Today, I believe I cannot make a difference.	Strongly disagree	Disagree	Agree	Strongly agree
3. Today, I believe that things will improve.	Strongly disagree	Disagree	Agree	Strongly agree
4. Today, I believe I am powerless to change my future.	Strongly disagree	Disagree	Agree	Strongly agree
5. Today, I see my future as gloomy.	Strongly disagree	Disagree	Agree	Strongly agree
6. Today, I believe I will accomplish what I set out to do.	Strongly disagree	Disagree	Agree	Strongly agree
7. Today, I believe I can help improve things.	Strongly disagree	Disagree	Agree	Strongly agree
8. Today, I feel giving up would be easier.	Strongly disagree	Disagree	Agree	Strongly agree
9. Today, I believe I can overcome obstacles.	Strongly disagree	Disagree	Agree	Strongly agree
10. Today, things will not work out as I would like.	Strongly disagree	Disagree	Agree	Strongly agree

Self-assessment (State-Trait Hopelessness) Scale

Part 2 of 2

DIRECTIONS: A number of statements, which people may use to describe their thoughts, are given below. Read each statement and then circle the response to the right of the statement that best describes how you typically think—or how you have thought over the years. There are no right or wrong answers. All of your information will be kept confidential.

Typically (Over the years)...

1. Typically, things do not work out as I would like.	Strongly disagree	Disagree	Agree	Strongly agree
2. Typically, I believe I can overcome obstacles.	Strongly disagree	Disagree	Agree	Strongly agree
3. Typically, I see myself as fortunate.	Strongly disagree	Disagree	Agree	Strongly agree
4. Typically, I see my future as gloomy.	Strongly disagree	Disagree	Agree	Strongly agree
5. Typically, negative things seem to happen to me.	Strongly disagree	Disagree	Agree	Strongly agree
6. Typically, it is difficult for me to imagine my future.	Strongly disagree	Disagree	Agree	Strongly agree

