- (6) Some post-graduate college work (masters, doctoral)
- (7) Graduate with masters- or doctoral-level degree

8. What is your current job status?

- (1) Employed full-time
- (2) Employed part-time
- (3) Retired
- (4) Disabled or unable to work
- (5) Student
- (6) Other (please list) _____

9. What type of health insurance do you have?

- (1) Medicare
- (2) Medicaid
- (3) Government VA
- (4) Employer provided
- (5) Privately purchased
- (6) No health insurance

D4: Patient Health Questionnaire

Patient Health Questionnaire (PHQ-9)

1. Little interest or pleasure in doing things	not at all	several days	more than half the days	nearly every day
2. Feeling down, depressed or hopeless	not at all	several days	more than half the days	nearly every day
3. Trouble falling or staying asleep, or sleeping too much	not at all	several days	more than half the days	nearly every day
4. Feeling tired or having little energy	not at all	several days	more than half the days	nearly every day
5. Poor appetite or overeating	not at all	several days	more than half the days	nearly every day
6. Feeling bad about yourself, or that you are a failure or have let yourself or your family down	not at all	several days	more than half the days	nearly every day
7. Trouble concentrating on things, such as reading the newspaper or watching television	not at all	several days	more than half the days	nearly every day
8. Moving or speaking so slowly that other people could have noticed? Or the opposite - being so fidgety or restless that you have been moving around a lot more than usual.	not at all	several days	more than half the days	nearly every day
9. Thoughts that you would be better off dead or of hurting yourself in some way	not at all	several days	more than half the days	nearly every day
10. If you checked off any problems, how difficult have these problems made it for you to do your work, take care of things at home, or get along with other people?	not difficult at all	somewhat difficult	very difficult	extremely difficult

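### The Week 2 call script opens the suicide questions only on a hopelessness score of 1.8 or higher and does not link a positive PHQ-9 item 9 to them

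*Combined protocol and SAP*

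**What the plan says.** Section 5.0 has the PI make the Week 2 call to the PI's own participants and follow a script. Appendix B1 is that script. After the monitor instructions it runs: demographics, hopelessness scale, suicidal ideation screening, PHQ-9, social support, adverse-event check, return of monitors.

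The suicidal ideation block is conditional: "To be completed only if participant scores 1.8 or higher on the self-assessment questionnaire". Inside it, the caller asks the suicide questions, "following instructions in the virtual suicide protocol based on patient risk level". B1 invokes that protocol nowhere else.

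The PHQ-9 follows: "how often have you been bothered by any of the following problems? (Ask patient the questions in questionnaire and chart answers in REDCap". No further instruction is attached. Item 9 in Appendix D4 reads "Thoughts that you would be better off dead or of hurting yourself in some way".

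Near the end of the call there is a check that does not depend on any score: "At the end of every visit, I like to check in and make sure you have not experienced any of the following". Section 11.3 names suicidal ideation as an adverse event. It also sets out PI monitoring during data collection, immediate response by the PI, a report to the advisor (immediately, and within 24 hours), possible safety committee review, and notice to primary care if clinical status is affected. Section 6.0 adds that a participant who shows apprehension may choose "to be referred to their physician for further counseling follow-up".

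**The concern.** The study puts a direct question about self-harm to every participant it calls and already has a structured response to suicidal thoughts. The script connects the two only through the hopelessness score, which is taken before the self-harm question is asked.

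This matters most for the PI's own group. Appendix A1 admits to the PI's study only patients whose hospital state hopelessness score was below 1.8, the same value that opens the suicide block at Week 2. Those still below it will skip the block. The protocol gives no ground for treating a low hopelessness score as ruling out a positive item 9. Section 1.0 describes the risk from hopelessness as independent of depression, and Sections 5.0 and 8.0 measure depressive symptoms separately as a covariate.

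What is at stake is the quality of the immediate safety response on the call. No estimate or test in the plan depends on it.

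**Working it through.** The plan gives no figure to reproduce. The check is a walk through B1 for each combination of hopelessness score and item 9 answer.

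| Week 2 hopelessness score | PHQ-9 item 9 | What B1 directs | With the added line |
|---|---|---|---|
| 1.8 or higher | any answer | Suicide questions and protocol, before the PHQ-9 | Unchanged |
| Below 1.8 | not at all | No suicide questions | Unchanged |
| Below 1.8 | any other answer | Chart the answer and go on to social support; adverse-event check at the end of the call | Suicide questions and protocol, directly after the PHQ-9 |

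Only the third row shows a gap. Sections 5.0, 6.0 and 11.3 and the other appendices contain no rule tied to item 9.

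**Which score opens the block.** B1 refers to the self-assessment questionnaire. Appendix D1 gives that title to the scale as a whole ("Self-assessment (State-Trait Hopelessness) Scale Part 1 of 2"), and Table 1 scores the state and trait parts separately: "Adding the item scores and dividing by the number of items provides a total score for each subscale". The value 1.8 is defined only for the 10-item state score, in Appendix A1. B1 does not say whether state, trait or either counts. The gap exists on any of these readings, so the fix need not choose between them.

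**How many could be affected.** Inputs:

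- n = 45, the PI-enrolled participants (Sections 1.0 and 5.0). This is a ceiling, because anyone at 1.8 or higher at Week 2 is already asked the suicide questions. The call procedures of the parent study are not in this document, so its participants are not counted.
- p, the chance that a participant below 1.8 endorses item 9. The documents give no value; the values below are assumptions.

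Expected cases = n × p. Chance of at least one = 1 − (1 − p)^n.

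| Assumed p | Expected cases | Chance of at least one |
|---|---|---|
| 0.1% | 45 × 0.001 = 0.045 | 1 − 0.999^45 = 4.4% |
| 1% | 45 × 0.01 = 0.45 | 1 − 0.99^45 = 36% |
| 5% | 45 × 0.05 = 2.25 | 1 − 0.95^45 = 90% |
| 10% | 45 × 0.10 = 4.5 | 1 − 0.90^45 = 99% |

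The assumed rate drives the answer almost entirely, so the table shows only that the documents cannot settle the count. The case rests on the missing link.

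**The case against.** The strongest reply is that a positive item 9 would be handled anyway. Section 11.3 names suicidal ideation as an adverse event and places written duties on the PI, who is also the caller for this group: monitoring during data collection, an immediate response, and a report to the advisor within 24 hours. The end-of-call check is open to everyone. Section 10.0 records that both IRBs approved the study. Most of this stands. A reader might infer that a disclosure would go unanswered, or that the response would rest on the caller's judgment alone; these written duties do not support either reading. They do not, however, mention item 9, do not say that a positive answer counts as an adverse event, and do not open the suicide questions or the risk-level instructions during the call. IRB approval is relevant context but does not supply the missing line.

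A second reply is that the virtual suicide protocol or the adverse-event question list may already contain an item 9 rule. That is possible, as neither is reproduced. A reader might infer that the study has no such rule anywhere, or that any such rule would contradict B1. The documents show neither. The word 'only' governs the suicidal ideation block, and a later adverse-event question with its own follow-up could sit beside it without conflict. The point is therefore confined to B1 as shown.

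A third reply is that few people are affected. That is probably right, and it bears on how serious the point is. It does not weigh much against a one-line change.

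**Conclusion.** The point holds in a limited form. B1 as shown asks the suicide questions and opens the suicide protocol only at a hopelessness score of 1.8 or higher, does so before the PHQ-9, and links a positive item 9 to neither. A participant below 1.8 who endorses item 9 is left to the general adverse-event route, which is real but does not name the structured questions.

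The number affected is at most 45, probably small, and cannot be estimated from the documents. Aims 1 to 3 are untouched. The conclusion assumes that the caller follows the script, as Section 5.0 requires, and that no unseen document already adds the step. It is a safety point in a call script that should be fixed. It is not a flaw in the design or the analysis.

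**What to change.** Leave the 1.8 trigger exactly as the study now applies it, including whichever subscale it uses, and keep the block where it is. Delete the word 'only' from its instruction. Directly after the PHQ-9 in B1, add:

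*If item 9 is answered anything other than 'not at all' and the suicide ideation questions have not already been asked, complete them now and follow the virtual suicide protocol.*

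If the suicide protocol or the adverse-event list already provides for this, the same line brings B1 into step with it.

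The cost is a script amendment with IRB approval and a few extra minutes for the few participants who trigger the step. It needs no new instrument or staff. Everyone screened under the current trigger is still screened at the same point in the call.
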